9.3.2 Laboratory Evaluations

Samples for laboratory assays will be sent to a central laboratory for analysis (unless noted otherwise). Detailed instructions for the collection, processing, and shipment of laboratory samples will be provided by the sponsor and the central laboratory. The investigator is responsible for reviewing laboratory results for clinical significance.

The following laboratory evaluations will be conducted during the study:

- Pregnancy test(s): Female subjects of childbearing potential (ie, are not surgically sterile or postmenopausal) must participate in pregnancy test(s).
 - A serum pregnancy test should be performed within 4 to 8 days prior to the baseline (Day 1) visit to allow sufficient time to obtain the pregnancy test results prior to randomization on Day 1. The results must be available and negative before the subject initiates study drug.
 - If the serum pregnancy test takes place more than 8 days prior to Day 1, then one of the following tests should be conducted:
 - Subjects who produce urine will participate in a urine pregnancy test on Day 1. The results must be available and negative before the subject initiates study drug.
 - Subjects who cannot produce urine will be asked to return to the study site within 4 to 8 days prior to Day 1 for an unscheduled serum pregnancy test. The results must be available and negative before the subject initiates study drug.
 - Serum pregnancy test samples will be analyzed by the central lab and urine pregnancy test samples will be analyzed by the local lab.
 - Additional pregnancy tests may be conducted during the study to establish the absence of pregnancy based on the investigator's clinical judgment or as required by local regulations.
- CBC: A CBC with differential will be performed at the baseline (Day 1) visit and at the Week 20 (or EOT) visit. At the other visits including the screening visits, a CBC without differential will be performed. CBC with differential will include: Hb, hematocrit, RBC count, mean corpuscular volume, mean corpuscular Hb, mean corpuscular Hb concentration, red cell distribution width, white blood cell count with differential (neutrophils, lymphocytes, monocytes, eosinophils, and basophils), and platelets.

Hemoglobin will be monitored throughout the study to determine the dose of study medication (vadadustat or epoetin alfa) that subjects should receive. Refer to Section 8.3.5 Hb levels can be measured more frequently based on investigator's clinical judgment.

• Reticulocyte count: An automated reticulocyte count (both absolute and percent) will be performed.

- Coagulation tests: Blood sample will be collected to assess the prothrombin time, partial thromboplastin time, and international normalized ratio (INR).
- Folate and vitamin B12: Blood sample will be collected to assess folate and vitamin B12 levels.
- C-reactive protein: Blood sample will be collected to assess CRP.
- Serum chemistry: Blood sample will be collected to assess sodium, potassium, bicarbonate, chloride, calcium, magnesium, phosphorus, glucose, creatinine, blood urea nitrogen, creatine phosphokinase, uric acid, albumin, and total protein.
- Liver function tests: Blood sample will be collected to assess total bilirubin, alkaline phosphatase, ALT/SGPT, AST/SGOT, and lactate dehydrogenase.
- Iron indices: Blood samples will be collected to assess the following indices: ferritin, iron, TIBC, and TSAT.
- Lipid panel: Blood sample will be collected to assess total cholesterol, low density lipoprotein (LDL), high density lipoprotein (HDL), and triglycerides.
- PK evaluations (for subjects in the vadadustat treatment arm): Plasma samples will be analyzed for vadadustat and its metabolites. Detailed instructions for collection, processing, storage, and shipment of the samples for PK and metabolite analyses will be provided by the sponsor or a designated laboratory.
- Additional biomarkers: Blood samples for additional biomarker analysis (eg, hepcidin and VEGF) will be collected.
- Erythropoietin: Blood samples for analysis of EPO levels will be collected.
- Exploratory analyses: Additional blood samples may be collected for exploratory analyses of biomarkers (eg, factors relating to the activation of the HIF pathway). Subjects will also be asked to provide optional written informed consent to obtain and store a blood sample for future genetic analyses.

9.3.3 Procedures Related to Study Drug Treatments

- Epoetin alfa dosing (for epoetin alfa treatment arm only): See Section 8.3.4 for additional information.
- Epoetin alfa dose reduction (for vadadustat treatment arm only): See Section 8.3.5 for additional information.
- Vadadustat dosing (for vadadustat treatment arm only): See Section 8.3.5 for additional information.
- Vadadustat drug dispensation (for vadadustat treatment arm only): See Section 8.2.2 for additional information.
- Review vadadustat dosing instructions (for vadadustat treatment arm only): See Section 8.3.5 for additional information.
- Vadadustat drug reconciliation (for vadadustat treatment arm only): See Section 8.2.2 for additional information.

- Review vadadustat dosing compliance (for vadadustat treatment arm only): Subjects will be questioned regarding dosing compliance. See Section 8.3.7 for additional information.
- Resuming dosing with epoetin alfa (or another ESA) (for vadadustat treatment arm only): See Section 8.3.5 for additional information.
- Recording of use of rescue therapy (RBC transfusions and epoetin alfa rescue therapy): See Section 8.3.10 for additional information.
- Recording of use of supplemental iron: See Section 8.3.9 for additional information.
- Recording of use of therapeutic phlebotomy: See Section 8.3.11 for additional information.

9.4 Schedule of Activities

The Schedule of Events in Appendix A shows the timing of planned study procedures.

Subjects will take study drug per their treatment randomization.

Every effort should be made to adhere to this procedure schedule and the planned assessments should be completed at each study visit.

NOTE: If possible, study visits should be scheduled on the day of the first hemodialysis session of the week to allow for the turnaround time for central lab Hb values (and dose adjustment as needed) before the end of the workweek.

9.4.1 Screening Visits

Screening visits must be performed within 4 weeks prior to dosing on Day 1 and the last screening visit must be completed at least 4 days before dosing starts on Day 1 to allow for laboratory test results to be available prior to initiation of study drug.

For eligibility purposes, if Hb at SV1 is 10.0 to 10.5 g/dL, 1 retest CBC should be performed prior to SV2. If the retest Hb is \geq 10.0 g/dL, the subject should not proceed with SV2. If the Hb at SV1 is >10.5 g/dL, the subject should not proceed with any further screening procedures at that time.

Subjects will continue their epoetin alfa dosing regimen during the screening period.

At SV1, the following activities/procedures will be performed:

- Signing of informed consent
- In addition, subjects may be asked during screening or at any study visit thereafter to provide optional written informed consent to obtain and store a blood sample for future genetic analyses.
- Review of study inclusion and exclusion criteria
- Review acceptable methods of contraception
- Vital signs
- Laboratory procedures (if blood samples are collected on a day of dialysis, blood draws should be done prior to dialysis, if applicable):
 - o CBC
 - Iron indices
- Epoetin alfa dosing will continue

At SV2, the following activities/procedures will be performed:

- Review of study inclusion and exclusion criteria
- Review acceptable methods of contraception
- Demographics, medical history, and physical examination
- Vital signs
- Review of concomitant medications
- Laboratory procedures (if blood samples are collected on a day of dialysis, blood draws should be done prior to dialysis, if applicable):
 - Serum pregnancy test (see Section 9.3.2 for additional information)
 - o CBC
 - Folate and vitamin B12 levels
 - Serum chemistry
 - Liver function tests
- Epoetin alfa dosing will continue

9.4.2 Baseline Visit (Day 1)

There must be a minimum of 4 days between the last screening visit and the baseline visit.

On Day 1, blood sample collection and other baseline procedures should be completed prior to dosing with study drug (vadadustat or epoetin alfa). On Day 1, study drug will be administered at the investigative site, and may be administered prior to or during the dialysis session.

At the baseline visit, the following activities/procedures will be performed:

- Review of study inclusion and exclusion criteria
- Review acceptable methods of contraception
- Subject randomization
- Dry weight and dialysis treatment review
- Dialysis adequacy (from dialysis performed during screening)
- Vital signs
- 12-lead ECG (ECGs should be completed prior to blood draws when possible and should be obtained after the subject has been resting supine comfortably for approximately 10 minutes; ECG may be completed and reviewed by the investigator on Day 1 or if needed for scheduling reasons [eg, dialysis treatment is scheduled for early morning of Day 1], the ECG can be completed and reviewed up to 1-3 days prior to Day 1)
- AE review
- Recording of any concomitant medication use since screening visit
- Laboratory procedures (if blood samples are collected on a day of dialysis, blood draws should be done prior to dialysis, if applicable):
 - Urine pregnancy test (see Section 9.3.2 for additional information)
 - CBC with differential
 - Reticulocyte count
 - Coagulation tests
 - C-reactive protein
 - Serum chemistry
 - Liver function tests

- Iron indices
- Lipid panel
- Sample for PK analysis (vadadustat treatment arm only; the sample will be collected between 30 minutes to 1 hour after vadadustat administration either prior to or during dialysis; the time of the vadadustat dose, the PK sample collection time, and the start and stop times of the dialysis session will be documented)
- Biomarkers
- o Sample for erythropoietin measurement
- Sample for exploratory analyses
- Subjects in epoetin alfa treatment arm will continue to receive epoetin alfa
- For subjects in the vadadustat treatment arm only:
 - Initiate vadadustat dosing
 - Vadadustat drug dispensation
 - o Review vadadustat dosing instructions
- Review use of rescue therapy (RBC transfusions and epoetin alfa rescue therapy)
- Review use of iron supplementation

9.4.3 Week 2, 4, 6, 8, 10, 12, 14, 16, and 18 Visits

At the Week 2 and Week 18 visits, subjects in the vadadustat treatment arm should be reminded and instructed to hold their vadadustat dose on the day of the Week 4 and Week 20 visits (respectively), as blood sample for PK analysis will be collected on the day of the Week 4 and Week 20 visits prior to vadadustat administration at the investigative site.

The following activities/procedures will be performed at the visits on Week 2, 4, 6, 8, 10, 12, 14, 16, and 18, unless noted otherwise:

- Review acceptable methods of contraception
- Dry weight and dialysis treatment review
- Dialysis adequacy (Week 8 only)
- Vital signs
- AE review
- Concomitant medication review
- Laboratory procedures (if blood samples are collected on a day of dialysis, blood draws should be done prior to dialysis, if applicable):
 - o CBC
 - Reticulocyte count (Weeks 4, 8, 12, and 16 only)
 - C-reactive protein (Week 8 only)
 - Serum chemistry (Weeks 4, 8, and 16 only)
 - Liver function tests (Weeks 4, 8, and 16 only)
 - Iron indices (Weeks 8 and 16 only)
 - 2 samples for PK analyses (Week 4 only; vadadustat treatment arm only; the first sample will be collected prior to vadadustat administration and the second sample will be collected at least 15 minutes post dialysis. If post dialysis collection is not possible, the second PK sample will be collected at least 3 hours after vadadustat administration. The time of the last dose of vadadustat taken prior to the PK sampling, as well as the timing of the PK sample collection, will be documented)

- Biomarkers (Week 8 only)
- Sample for erythropoietin measurement (Weeks 8 and 16 only)
- Sample for exploratory analyses (Week 8 only)
- Subjects in epoetin alfa treatment arm will continue to receive epoetin alfa
- For subjects in the vadadustat treatment arm only:
 - Vadadustat dosing
 - Vadadustat drug dispensation (Weeks 4, 8, 12, 16, and other visits as applicable)
 - Review vadadustat dosing instructions
 - Vadadustat drug reconciliation (Weeks 4, 8, 12, 16, and other visits as applicable)
 - o Review vadadustat dosing compliance
- Review use of rescue therapy (RBC transfusions and epoetin alfa rescue therapy)
- Review use of iron supplementation
- Review use of therapeutic phlebotomy

9.4.4 Week 20 Visit (End-of-Treatment)

On the day of the Week 20 visit, the vadadustat dose will be taken at the investigative site after a blood sample for PK analysis has been collected.

At the Week 20 visit, the following activities/procedures will be performed:

- Review acceptable methods of contraception
- Dry weight and dialysis treatment review
- Dialysis adequacy
- Vital signs
- AE review
- Concomitant medication review
- Laboratory procedures (if blood samples are collected on a day of dialysis, blood draws should be done prior to dialysis, if applicable):
 - CBC with differential
 - o Reticulocyte count
 - C-reactive protein
 - Serum chemistry
 - Liver function tests
 - \circ Iron indices
 - Lipid panel
 - 2 samples for PK analyses (vadadustat treatment arm only; the first sample will be collected prior to vadadustat administration and the second sample will be collected at least 15 minutes post dialysis. If post dialysis collection is not possible, the second sample will be collected at least 3 hours after vadadustat administration. The time of the last dose of vadadustat taken prior to the PK sampling, as well as the timing of the PK sample collection, will be documented)
 - Biomarkers
 - Sample for erythropoietin measurement
 - Sample for exploratory analyses
- Subjects in epoetin alfa treatment arm will continue to receive epoetin alfa

- For subjects in the vadadustat treatment arm only:
 - Vadadustat drug reconciliation
 - Review vadadustat dosing compliance
 - Resume dosing with epoetin alfa (or another ESA): After the end of vadadustat treatment at Week 20 (or following early discontinuation of vadadustat), subjects may resume dosing with epoetin alfa (or another ESA), based on the approved label for adult patients with CKD on dialysis
- Review use of rescue therapy (RBC transfusions and epoetin alfa rescue therapy)
- Review use of iron supplementation
- Review use of therapeutic phlebotomy

9.4.5 Week 24 Visit

At the Week 24 visit, the following activities/procedures will be performed:

- AE review
- Concomitant medication review
- Laboratory procedures (if blood samples are collected on a day of dialysis, blood draws should be done prior to dialysis, if applicable):
 - o CBC
 - C-reactive protein
 - Serum chemistry
 - Liver function tests
 - Iron indices
 - Biomarkers
- All subjects will continue to receive epoetin alfa (or another ESA), based on the approved label for adult patients with CKD on dialysis
- Review use of rescue therapy (RBC transfusions and epoetin alfa rescue therapy)
- Review use of therapeutic phlebotomy

10 ADVERSE EVENTS

10.1 Definitions

10.1.1 Adverse Events (AEs)

For the purposes of this study, an AE is any untoward medical occurrence (including a clinically significant abnormal laboratory finding) that occurs in the protocol-specified AE reporting period; the event does not necessarily have a causal relationship with that treatment or usage.

An AE includes medical conditions, signs, and symptoms not previously observed in the subject that emerge during the protocol-specified AE reporting period, including signs or symptoms associated with pre-existing underlying conditions that were not present prior to the AE reporting period.

Adverse events therefore include the following:

• All AEs, whether suspected to be causally related to study drug or otherwise

- All AEs secondary to any medication overdose, medication error, abuse, withdrawal, sensitivity, or toxicity
- Illnesses apparently unrelated to study drug, including the worsening of a pre-existing illness (see paragraph below on Pre-Existing Conditions).
- Injury or accidents. Note that if a medical condition is known to have caused the injury or accident (eg, a fall secondary to dizziness), the medical condition (dizziness) and the accident (fall) should be reported as 2 separate AEs.
- Abnormalities in physiological testing or physical examination findings that require clinical intervention or further investigation (beyond ordering a repeat [confirmatory] test).
- Laboratory abnormalities that require clinical intervention or further investigation (beyond ordering a repeat [confirmatory] test) unless they are associated with an already reported clinical event. Laboratory abnormalities associated with a clinical event reported as an AE (eg, elevated liver enzymes in a subject with jaundice) should be described under 'Comments' on the report of the clinical event rather than reported as separate AEs.

The following guidelines are to be used when reporting AEs for this study:

Medical Diagnoses – Whenever possible, a medical diagnosis term should be used to report AEs instead of signs and symptoms due to a common etiology, as determined by qualified medical study staff. For example, pneumonia should be the reported AE term, instead of fever, dyspnea, etc., when the diagnosis has been established. Signs and symptoms should be reported as event terms only when the medical diagnosis remains unknown, and revised to a medical diagnosis term once it has been established.

Procedures – Diagnostic and therapeutic non-invasive and invasive procedures, such as surgery, should not be reported as AEs. However, the medical condition for which the procedure was performed should be reported if it meets the definition of an AE. For example, an acute appendicitis that begins during the AE reporting period should be reported as the AE and the resulting appendectomy noted under "Comments."

Pre-planned therapeutic procedures not associated with a new medical condition or worsening pre-existing condition should not be reported as AEs.

Kidney Transplantation – A kidney transplant will not be recorded as an AE. Subjects who discontinue study drug because of receipt of a kidney transplant should continue with the Schedule of Activities (Appendix A).

Pre-Existing Conditions – In this study, a pre-existing condition (ie, a disorder present before the AE reporting period started and noted on the pre-treatment medical history/physical examination form) should not be reported as an AE unless the condition worsens or episodes increase in frequency during the AE reporting period.

Abnormal Test Findings – All laboratory test results will be reviewed by the investigator. Investigators will utilize their judgment in determining if out of range laboratory values are clinically significant and should denote this using the abbreviation "CS" on the laboratory report for source documentation. Laboratory tests that are labeled as clinically significant should be reported as AEs, either separately or as part of a description of a symptomatic AE. If there are significant changes in a laboratory report from a previous visit that are determined to be clinically significant, these should also be reported as AEs. Any abnormal laboratory value which requires treatment or further diagnostic testing or results in discontinuation from study should be reported as AEs. An expected laboratory abnormality from a condition that is part of the medical history is not considered clinically significant for the purposes of the study unless it represents a worsening of the condition.

Abnormalities in ALT, AST and Total Bilirubin – Abnormalities in ALT, AST and total bilirubin should be reported to the sponsor's medical monitor (or medical director) or contract research organization (CRO) designee within 24 hours of awareness as a serious adverse event (SAE) with 'other medically important event' criterion selected, if the following conditions are met:

- New elevation in ALT or AST >3 times ULN, with or without an elevation of total serum bilirubin >2 times ULN, AND
- No other reason was identified that explains the increased ALT/AST with or without an increased bilirubin (eg, viral hepatitis, acute liver disease).

If new elevations in ALT or AST >3 times ULN, with or without an elevation of total serum bilirubin >2 times ULN are identified, the following steps are to be taken:

- Temporary discontinuation of study medication
- Repeat testing of ALT, AST, ALP, and total bilirubin, to be completed within 48 to 72 hours to confirm the abnormalities and to determine trend
- Study medication should not be resumed until monitoring indicates abnormalities have resolved, are stable, or are not rapidly increasing

Worsening of Anemia – In this study, it is possible that some subjects may experience a worsening of anemia. Worsening of anemia should not be considered an AE unless the worsening of anemia is associated with a cause other than the subject's CKD.

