10.1.2 Serious Adverse Events (SAEs)

Each AE must be classified by the investigator as SERIOUS or NONSERIOUS. An AE that meets 1 or more of the following criteria (or outcomes) is classified as serious:

- Death
- Life-threatening (see paragraph below on Life-threatening)
- In-patient hospitalization or prolongation of existing hospitalization (see paragraph below on Hospitalization)
- Persistent or significant disability or incapacity (see paragraph below on Disability)
- Congenital anomaly or birth defect
- Is considered a medically important event not meeting the above criteria, but which may jeopardize a subject, or may require medical or surgical intervention to prevent one of the criteria listed in this definition.

Serious also includes any other event that the investigator or sponsor judges to be serious. If there is any doubt whether the information constitutes an AE or SAE, the information is to be treated as an SAE.

Life-threatening – Any event in which the subject was at risk of death at the time of the event; 'life-threatening' does not refer to an event which hypothetically might have caused death if it were more severe. For example, drug-induced hepatitis that resolved without evidence of hepatic failure would not be considered life threatening, even though drug-induced hepatitis of a more severe nature can be fatal.

Hospitalization – Hospitalization is defined as an overnight admission with observation of a minimum of 24 hours. A hospitalization planned before the start of the study for a pre-existing condition that has not worsened during the AE reporting period does not constitute an SAE unless an untoward event occurs related to the procedure (eg, elective hospitalization for a total knee replacement due to a preexisting condition of osteoarthritis of the knee that has not worsened during the study).

Disability – Defined as a substantial disruption in a person's ability to conduct normal life functions.

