11.1 Sample Size Determination

About 50 subjects (n=25 per treatment arm) are planned for randomization in the study.

Sample size has been determined to reflect the exploratory nature of this study.

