11.6 Efficacy Analyses

This study is exploratory in nature, designed to evaluate the change in Hb from baseline over time during the treatment period. No formal statistical testing will be performed.

Summary statistics (mean, median, standard deviation [SD], range, proportion and 95% confidence intervals when appropriate) will be provided, by treatment groups for primary and secondary endpoints.

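### Section 10.1.1 gives unreconciled reporting rules for raised ALT/AST with jaundice, and an exception loose enough to cover drug-induced injury, so the automatic SAE flag and 24-hour notice can be missed or vary between sites

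*Combined protocol and SAP*

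**What the plan says.** All the reporting text at issue is in Section 10.1.1 of the protocol.

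- **General laboratory rule** (list of what counts as an AE). A laboratory abnormality tied to a clinical event already reported as an AE is not reported separately. The example is a liver one: "elevated liver enzymes in a subject with jaundice) should be described under 'Comments' on the report of the clinical event".
- **Medical Diagnoses paragraph.** Sites should report a diagnosis where they can, in place of its signs and symptoms.
- **Abnormal Test Findings paragraph.** A clinically significant laboratory result is an AE, reported either on its own or within the description of a symptomatic AE.
- **Paragraph on ALT, AST and total bilirubin.** These abnormalities go to the sponsor or its designee "within 24 hours of awareness as a serious adverse event (SAE) with 'other medically important event' criterion selected" when two conditions hold. The first is "New elevation in ALT or AST >3 times ULN, with or without an elevation of total serum bilirubin >2 times ULN, AND". The second is "No other reason was identified that explains the increased ALT/AST with or without an increased bilirubin (eg, viral hepatitis, acute liver disease").

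Section 10.1.2 lists the general seriousness criteria, including medically important events, and resolves doubt between AE and SAE in favour of SAE. Section 11.7 has all AEs coded in MedDRA and lists summaries of SAEs, related AEs and AEs leading to discontinuation of study drug. It names no ALT, AST or bilirubin threshold summary and no grouped hepatic summary.

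**The concern.** A fixed liver threshold is useful because it replaces site judgement with a number. Two features of the text bring the judgement back.

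First, the general rule's chosen example is close to the case that the liver rule was written for. A site with a jaundiced subject and raised enzymes finds one instruction to put the enzymes in a comment and another to report them as an SAE. Nothing says which governs.

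Second, the exception offers acute liver disease as a qualifying explanation without requiring that its cause be something other than study drug. Drug-induced liver injury can be called an acute liver disease, and the Medical Diagnoses paragraph encourages sites to move from findings to a diagnosis. Read literally, naming the disease ends the automatic report even when its cause is unknown or possibly the drug.

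At stake are the SAE flag, prompt notice to the sponsor, and a consistent count of enzyme elevations. The study is open-label (Section 8.3.2), so staff who make the choice know the treatment.

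**Working it through.** The plan states no figure on this point. It is descriptive ("No formal statistical testing will be performed", Section 11.6), and its sample size has no power basis. The check is therefore to apply the written rules to three subjects, each with a new ALT or AST above 3 x ULN.

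**Case A: no jaundice, no cause found.** Both liver conditions hold, so an SAE report within 24 hours is required. No clinical event has been reported, so the Comments rule does not apply. There is no conflict.

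**Case B: jaundice, no cause found.** Jaundice is reported and coded as an AE. The liver rule still applies, because its first condition holds with or without raised bilirubin, so an SAE report is required. The Comments rule also applies, because the enzymes accompany a reported clinical event, and it says not to report them separately. A site that follows the Comments rule alone produces a coded jaundice AE, no enzyme term and possibly no SAE flag.

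**Case C: acute liver disease named.** The second liver condition fails as worded, so the automatic SAE report is not required. The named disease is still a coded AE, and it is an SAE if it meets any Section 10.1.2 criterion. Only the automatic route is lost. The hold and repeat-test steps in the same paragraph depend on the enzyme threshold alone. A subject can therefore enter those steps with no required 24-hour notice.

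| Case | In coded AE counts | Automatic SAE report | At risk |
|---|---|---|---|
| A | Yes | Required | Nothing |
| B | Yes | Required by the liver rule, obscured by the Comments rule | SAE flag, 24-hour notice, enzyme term |
| C | Yes | Not required | Automatic SAE flag, 24-hour notice |

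**Scale of one reclassification.** Section 11.1 plans 25 subjects per arm, so one subject is 1/25 = 4% of an arm. Exact (Clopper-Pearson) 95% limits:

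- 0/25: upper limit 1 − 0.025^(1/25) = 13.7%, giving 0 to 13.7%.
- 1/25: lower limit 1 − 0.975^(1/25) = 0.1%; upper limit 20.4%.

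The same shift follows from reclassifying any single SAE in an arm of this size. It does not estimate how often the ambiguity would matter.

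**The case against.** The strongest reply is that the rules can be read together. The Comments rule prevents a laboratory value from being listed twice. The liver paragraph concerns seriousness and notification, and it is the more specific text. A site could file one liver event, flag it as medically important, describe the enzymes within it, and satisfy both. Likewise, in a rule about study-drug safety, the natural sense of an alternative reason is one other than the drug, and viral hepatitis, the other example, fits that sense.

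There are also safeguards. Doubt resolves to SAE, and the hospitalization and medically-important criteria remain. Liver tests are scheduled at the second screening visit, baseline and Weeks 4, 8, 16, 20 and 24 (Appendix A), with central laboratory analysis as the default (Section 9.3.2). Laboratory values are a safety endpoint (Section 5.2), summarized and listed by subject (Section 11). An internal committee reviews safety data regularly (Section 6.1).

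Much of this stands. In particular, a reader might infer that the coded liver counts leave out the worse cases. The documents do not support that. The Comments rule operates only when a clinical event is itself reported, so jaundice or the named disease is already a MedDRA-coded AE. Raised bilirubin is expressly inside the SAE rule, and naming a disease removes one trigger but not SAE status.

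The reply does not close the gap. The harmonized reading is available but unstated, and a site following the protocol's own example has little reason to feel doubt. The medically-important criterion is discretionary, which is what the threshold was meant to avoid. Section 10.1.2 also says that "drug-induced hepatitis that resolved without evidence of hepatic failure would not be considered life threatening". That is only a definition of life-threatening, but it shows that a hepatitis managed without admission may depend on the discretionary criterion alone. Laboratory listings preserve the values. They do not restore the SAE flag or the prompt notice.

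**Conclusion.** The concern holds in a limited form. Section 10.1.1 does not reconcile the Comments rule with the liver SAE rule for a jaundiced subject, and its exception is worded widely enough to take in liver injury of unknown or possibly drug-related cause. The automatic SAE flag, the 24-hour notice and the enzyme-term count can be missed or applied differently across sites. Section 11.7 names no laboratory threshold summary that would show this.

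The effect cannot be sized from the documents, which give no liver-event rate. If one liver SAE in an arm of 25 were classified the other way, the arm's result would move by 4 percentage points, as shown above.

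The conclusion assumes that some sites would follow the text literally. The rules are the same for both arms. Differential application by arm is possible in an open-label study, but nothing in the documents shows that it would occur.

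**What to change.** The changes affect reporting and tabulation only.

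1. In Section 10.1.1, state that the ALT/AST/bilirubin rule takes precedence over the Comments rule, including when jaundice or another liver event is also reported. Replace the jaundice example with a non-hepatic one.
2. Limit the exception to a confirmed cause other than study drug, so that liver disease of unknown or possibly drug-related cause is still reported as an SAE.
3. In Section 11.7, tabulate by arm the number of subjects with ALT or AST above 3 x ULN, with and without bilirubin above 2 x ULN, from the laboratory data already collected. This count does not depend on how a site classified the event.

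The cost is two sentences in Section 10.1.1, site guidance and one table. No new data are needed. One liver episode might be listed twice, as a clinical event and as an enzyme SAE; counting subjects rather than events deals with that.
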